5.2 Subject Exclusion Criteria

All eligible patients from clinics randomized to the study will be included in the comparison of the two groups regardless of intervention compliance (intention-to-treat analysis).

Exclusion criteria will be minimal in this pragmatic trial. The collaborative model of care will not be implemented in patients younger than 18 years or older than 85 years of age or patients who have CKD stage 5/ERSD. Primary care practitioners have the option of not implementing the intervention on any of their patients if they believe benefit to be minimal or risk too high due to patient comorbidities. Patients also have the option to opt-out from the facilitated collaborative model of care.

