Appendix I: CHRONIC KIDNEY DISEASE (CKD) HYPERTENSION MANAGEMENT PROTOCOL

This protocol will be initiated as directed by CHRONIC KIDNEY DISEASE (CKD) CHRONIC DISEASE MANAGEMENT PROTOCOL.

Protocol will be reviewed every year.

RN will perform protocol with assistance from PA or NP at same clinical site.

PA or NP may suggest deviations from protocol as deemed clinically appropriate.

Orders (except medication orders) will be placed by RN in electronic medical record using "per protocol" order mode with physician, PA or NP as authorizing provider. Medication orders may be routed to provider as suggested per protocol, but medication and dose will ultimately be selected and ordered by provider. After medication orders are finalized by provider, RN will notify patient of final decision.

Goals/Background

1. Chronic Kidney Disease (CKD) is defined as (for the purposes of this protocol):
 - a. Glomerular Filtration Rate (GFR) < 60 mL/min
 - b. Or presence of proteinuria, defined as any one of the following:
 - i. Random Urine Protein/Creatinine Ratio > 200 mg/g
 - ii. Random Urine Microalbumin/Creatinine Ratio > 30 mg/g
 - iii. 24 hour Urine Protein > 150mg
 - iv. Urine dipstick protein (adjusted for specific gravity)
2. Blood pressure (BP) goals
 - a. For patients with CKD goal blood pressure is Systolic (SBP) < 140 mmHg AND Diastolic (DBP) < 90 mmHg
3. ACEi/ARB
 - a. All patients with chronic kidney disease (with or without proteinuria) should be treated with an angiotensin converting enzyme inhibitor (ACEi) or angiotensin receptor blocker (ARB).
 - b. Recommended ACEi: lisinopril
 - i. Starting dose 5mg once daily if GFR > 10 mL/min or 2.5mg if GFR < 10mL/min
 - ii. Maximum dose 40mg once daily
 - iii. Class-specific considerations. Be aware of these potential adverse effects when conduction follow-up of initiation or titration of this medication (details on the follow-up process are below).
 1. Elevated potassium (hyperkalemia)
 2. Reduction in kidney function (increase in creatinine or decrease in GFR)
 3. Dry cough

- 4. Facial swelling (angioedema)
- c. Recommended ARB: losartan
 - i. Starting dose 25mg once daily
 - ii. Maximum dose 100mg once daily
 - iii. Class-specific considerations. Be aware of these potential adverse effects when conduction follow-up of initiation or titration of this medication (details on the follow-up process are below).
 - 1. Hyperkalemia

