 - 2. Reduction in kidney function (increase in creatinine or decrease in glomerular filtration rate)
 - 3. Very rarely causes dry cough
 - 4. Facial swelling (angioedema)

RN BP ASSESSMENT

- 1. RN BP Assessment Visit
 - a. Pre-Visit Planning: perform 1-2 weeks prior to appointment.
 - i. Call patient
 - 1. Request patient bring all pill bottles to appointment.
 - 2. If patient has home blood pressure device, ask patient to bring home device and written home blood pressure log (after checking blood pressure twice daily for 1 week) to appointment.
 - ii. GFR Assessment
 - 1. Review prior labs in "Results Review".
 - 2. Review last potassium, creatinine and glomerular filtration rate (GFR) in last 6 months.
 - 3. If all present within 6 months, no further action needed for GFR assessment.
 - 4. If no creatinine and GFR in last 6 months, order "CREATININE with-GFR".
 - 5. If no potassium in last 6 months, "POTASSIUM LEVEL".
 - 6. Compare most recent GFR with second most recent GFR. If most recent GFR is > 20% lower, discuss with provider.
 - 7. If GFR < 60 but >/= 30, update problem list to include "CKD Stage 3"
 - 8. If GFR < 30 but >15, update problem list to include "CKD Stage 4".
 - 9. If GFR < 15, update problem list to include "CKD Stage 5"
 - iii. Proteinuria Assessment
 - 1. Review prior urine protein testing in "Results Review" for following results in last 1 year:
 - a. Microalbumin/Creatinine Ratio, Urine, Random
 - b. Protein, Urine and Creatinine, Urine (both are required as ratio must be calculated manually by dividing urine

- protein by urine creatinine).
- c. Protein, 24 hour, Urine
- d. Urine dipstick protein (adjusted for specific gravity)
- 2. If labs are present in last year, no further action is needed for Proteinuria Assessment.
- 3. If none are available, order MICROALBUMIN/CREATININE RATIO

NOTE: "Unable to calculate" for Microalbumin/Creatinine Ratio implies zero protein present in urine.

- b. Assessment of BP goal
Goal blood pressure is SBP < 140 mmHg AND DBP < 90 mmHg.
- c. Provide education annually on non-pharmacologic management of hypertension.
 - i. Low Sodium Diet
 - 1. Discuss with patient importance of low sodium diet included no added salt as well as checking labels for processed foods.
 - 2. Provide patient with Exit Care SmartText in Patient Instructions: DIET-2 GRAM LOW SODIUM (choose appropriate language).
 - 3. Refer to nutrition at same clinical site for further counseling as needed.

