- a If patient is already on ACEi or ARB but not at maximum tolerated dose (see above), increase dose to achieve SBP and DBP goal (as per ACEi/ARB PROTOCOL below)
- b If patient is on maximum tolerated dose of ACEi or ARB, proceed to NON ACEi/ARB PROTOCOL.
- c If patient is not on ACEi or ARB, confirm allergies with patient.
- d If no prior allergy or adverse reaction to ACEi or ARB, proceed to ACEi/ARB PROTOCOL.
- e If prior allergy to ACEi is cough, proceed to ACEi/ARB PROTOCOL.
- f If prior allergy or adverse reaction to ACEi or ARB other than cough, consult with provider safety of starting ACEi or ARB.
- g If after discussion with provider, ACEi and ARB are both considered contraindicated, update allergies as needed

and proceed to NON-ACEi/ARB PROTOCOL.

ACEi/ARB PROTOCOL

1. Consider this protocol active until completed.
2. Review "Results Review" for past potassium and creatinine (abbreviated as "Cr" and "K" respectively hereafter). If both are available, no further action is needed. If one or both is not available in last 3 months, order both CREATININE LEVEL and POTASSIUM LEVEL as appropriate (referred to as "Cr/K Check" hereafter).
 - a. Lab Results Interpretation
 - i. Is K > 4.9?
 1. Yes
 - a. Discuss with provider before starting or increasing ACEi or ARB.
 2. No
 - a. If not on ACEi/ARB, and no prior allergy to ACEi or ARB, route pended order to provider for lisinopril 5mg once daily and proceed to "Follow-Up" below.
 - b. If not on ACEi or ARB and prior cough due to ACEi but no other ACEi or ARB allergy, route pended order to provider for losartan 25mg once daily and proceed to "Follow-Up" below.
 - c. If already on ACEi or ARB, but not at maximum tolerated dose, increase dose and proceed to "Follow-Up" below.
 - d. If already on ACEi/ARB at maximum tolerated dose, consider this protocol COMPLETED and proceed to NON-ACEi/ARB PROTOCOL.
 - e. Follow-Up
 - f. Schedule RN BP Assessment Visit and Cr/K Check 1-3 weeks following initiation or dose increase. Request patient to have labs drawn prior to appointment.
 - b. K Interpretation
 - i. Is K > 5.4?
 1. Yes. Discuss with provider stopping ACEi/ARB
 2. No
 - ii. 1. Is K > 4.9?
 3. Yes
 - a. Continue ACEi/ARB at current dose.
 - b. Provide patient with low potassium diet handout
 - c. Order repeat POTASSIUM LEVEL in 1 week.
 - d. If K is not < 5.0 on repeat evaluation, discuss with provider.
 - e. If K is </= 4.9, proceed to Cr Interpretation.
 4. No - proceed to Cr Interpretation.

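### Appendix I sets the lisinopril starting dose by GFR in its Goals, but its order step pends one dose with no GFR condition, and neither fits cleanly with the stage 5 exclusion in Section 5.2

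*Combined protocol and SAP*

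**What the plan says.** Appendix I, Goals/Background, item 3b, makes the lisinopril starting dose depend on GFR: "Starting dose 5mg once daily if GFR > 10 mL/min or 2.5mg if GFR < 10mL/min".

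The step that the nurse carries out is in the ACEi/ARB PROTOCOL of the same appendix, under Lab Results Interpretation. The nurse looks "for past potassium and creatinine" and, if either is missing from the last 3 months, is told to "order both CREATININE LEVEL and POTASSIUM LEVEL as appropriate". The step then branches on one value, whether potassium exceeds 4.9. If it does not, the instruction is: "If not on ACEi/ARB, and no prior allergy to ACEi or ARB", then "route pended order to provider for lisinopril 5mg once daily".

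GFR does appear earlier in the nurse pathway. Pre-visit planning says "Review last potassium, creatinine and glomerular filtration rate (GFR) in last 6 months", orders a creatinine with GFR if none is on file, and sends a fall of more than 20% to the provider for discussion. It also stages the patient. At the lowest level, "If GFR < 15, update problem list to include" is followed by the stage 5 label and nothing else.

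Section 5.2 of the protocol says that the collaborative model will not be implemented in "patients who have CKD stage 5/ERSD".

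The opening of Appendix I leaves the final choice of drug and dose to the provider.

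**The concern.** A nurse who reads the Goals and a nurse who follows the order step would put different lisinopril starting doses before the provider for the same patient with a GFR below 10. The appendix itself lists hyperkalaemia and reduced kidney function as effects to watch for with this drug. Section 9.1 captures hyperkalaemia, acute kidney injury, large eGFR reductions and initiation of dialysis as safety events. An order step that disagrees with its own dose rule at the lowest GFR is therefore worth tidying, even if few patients ever reach it.

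The inconsistency also carries forward. When creatinine rises after initiation or an increase, the ACEi/ARB PROTOCOL has the nurse discuss halving the dose, or stopping the drug if the patient is at the starting dose. That rule works only if the starting dose is defined once.

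**Working it through.** No sample-size, power or event figure is involved. The check sets the two dose texts side by side and then asks who can reach the step where they differ.

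**1. Dose by GFR range**

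| GFR (mL/min) | Goals, item 3b | Order step | Result |
|---|---|---|---|
| above 10 | 5 mg once daily | 5 mg once daily | agree |
| exactly 10 | no dose given | 5 mg once daily | gap in the Goals |
| below 10 | 2.5 mg | 5 mg once daily | differ: 5 / 2.5 = 2 |

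**2. Effect on the creatinine rule.** Take a patient with GFR below 10 who was given the pended 5 mg. Under the order step, 5 mg is the starting dose, so a creatinine rise above 20% leads to a discussion of stopping. Under the Goals, 5 mg is twice the starting dose, so the same rise leads to a discussion of halving. The same event has two readings.

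**3. Comparison with the diuretic pathway.** The NON ACEi/ARB PROTOCOL splits the diuretic choice at GFR 30, and the DIURETIC PROTOCOL repeats that split where the drug is recommended. The lisinopril split is not repeated in its order step. This suggests an omission rather than a deliberate simplification, though the documents do not say.

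**4. Who can reach the conflict.** The patient must be above the blood pressure goal, not taking an ACEi or ARB, free of a relevant allergy, have potassium not above 4.9, and have a GFR below 10. Appendix I labels every GFR below 15 as stage 5, so everyone below 10 falls in the group that Section 5.2 keeps out of the model. At entry, then, the conflict should not arise.

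**5. A fall in GFR during the 12 months.** A drop from 15 or more to below 10 within one interval exceeds (15 − 10) / 15 = 33%, so the more-than-20% check sends it to the provider. A stepwise decline need not: 15 × 0.8 = 12 and 12 × 0.8 = 9.6 are two falls of exactly 20%, and neither exceeds the limit. In either case the discussion is about the fall and is not tied to the lisinopril dose.

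**6. Fit with Section 5.2.** If Section 5.2 applies throughout follow-up, Appendix I lacks a step that takes a stage 5 patient out, and its dose for GFR below 10 cannot be used in the trial. If it applies only at entry, a patient whose GFR falls can meet the two conflicting doses. Each reading leaves text to reconcile.

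**The case against.** The strongest reply is that the conflict lies wholly inside a group the protocol removes. Section 5.2 is not worded as a baseline-only rule and can be read to cover a patient who reaches stage 5 later. Appendix I is also started under a separate CKD chronic disease management protocol that is not among the documents, so an exit rule may exist there. Both points stand. They make the reach small and mean that continuation in the pathway is inferred from silence, not instructed. They do not make the two dose texts agree, and they leave unexplained why Appendix I carries a dose for GFR below 10 at all.

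A second reply is that the order is only pended. The provider chooses drug and dose, a PA or NP assists and may suggest deviations, and use of the protocols is optional for practitioners. This stands too. It limits the consequence, but the provider is still presented with one of two conflicting doses.

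Two stronger readings are tempting. A reader might infer that the nurse pathway ignores kidney function. It does not: the ACEi/ARB PROTOCOL reviews creatinine, pre-visit planning reviews GFR, and a fall above 20% goes to the provider. What is missing is a link from the GFR to the lisinopril order. A reader might also infer that patients with very low GFR will be given a conflicting dose. The documents show only a mismatch in what is pended; they do not show that any trial patient would meet all the conditions.

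The gap at exactly 10 is editorial by itself.

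**Conclusion.** The inconsistency is real and both texts are current. It is confined to GFR below 10, where the doses differ by a factor of two, plus the uncovered value of exactly 10. It makes the later starting-dose rule ambiguous in the same range, and Appendix I does not match Section 5.2 for a patient whose GFR falls into stage 5 during follow-up.

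The weight is minor. The number affected is probably very small, but it cannot be computed because the documents give no GFR distribution. The judgement assumes that Section 5.2 is applied at entry, that pre-visit GFR review takes place, and that providers check pended orders. The documents do not support calling this a demonstrated patient hazard or a flaw in the trial design. It is safety wording to correct, with no bearing on the primary outcome, power or analysis.

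**What to change.** The clinical leads should reconcile four places in Appendix I with one another and with Section 5.2: the Goals entry for lisinopril, the GFR assessment in pre-visit planning, the order step in the ACEi/ARB PROTOCOL, and the creatinine rule that refers to the starting dose. After the change:

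- the Goals and the order step should state the same starting-dose rule, covering every GFR value for which the appendix is meant to be used;
- the starting dose used in the creatinine rule should have one meaning;
- Appendix I should be consistent with the stage 5 exclusion, including for a patient whose GFR falls into that range during the 12 months.

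Any matching order set in the electronic record should be edited to agree. Which dose or rule is right is a clinical decision, and none is proposed here. The cost is a wording and order-set edit, with no change to sample size, data collection or analysis.

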- c. Serum Creatinine (Cr) Interpretation
 - ii. Is Cr >20% higher than value prior to initiation or last increase of ACEi/ARB?
 - 1. Yes. Discuss with provider decreasing dose by 50% (or stopping if at starting dose). Discuss follow up plan for Cr with provider as well.
 - 2. No
 - (i) Is creatinine within 30% of baseline since initiation?
 - (a) No. Discuss with provider decreasing dose by 50% (or stopping if at starting dose). Discuss follow up plan for Cr with provider as well.
 - (b) Yes. Proceed to RN BP Assessment.
 - 3. RN BP Assessment
 - a. Perform RN BP Assessment as detailed above.
 - b. Is BP at goal based on definitions above?
 - i. Yes. Continue regimen and schedule RN BP Assessment Visit in 3 months and follow-up with PCP within 6 months.
 - 1. If BP continues to be at goal in 3 months, this protocol is COMPLETE and can return hypertension management to PCP.
 - ii. No
 - 2. Is ACEi/ARB at maximum tolerated dose?
 - (i) Yes. This protocol is COMPLETE. Initiate NON-ACEi/ARB PROTOCOL.
 - (ii) No route pended order to provider for double prior dose of current ACE and return to "Follow-Up" above.

NON ACEi/ARB PROTOCOL

- 1. Discuss with provider selection of next anti-hypertensive protocol.
- 2. Discuss following medication suggestions with provider. These are only suggestions to guide management, but final selection is at provider's discretion.
 - a. If patient has history of myocardial infarction or heart failure, recommend BETA-BLOCKER PROTOCOL.
 - i. Recommend carvedilol given dual properties of heart rate reduction (beta blockade) and vasodilation (alpha blockade) and, therefore, typically greater impact on blood pressure.
 - ii. Recommended starting dose: carvedilol 6.25mg twice daily.
 - iii. Maximum dose: carvedilol 25mg twice daily.
 - iv. Class-specific considerations
 - 1. Low heart rate (bradycardia)
 - 2. Lower extremity swelling, erectile dysfunction, fatigue.
 - 3. Exacerbation of asthma or chronic obstructive lung disease symptoms (shortness of breath or wheezing).
 - b. If patient is on maximum tolerated beta-blocker or has no history of myocardial infarction or heart failure, recommend DIURETIC PROTOCOL.
 - i. For patients with GFR > 30 mL/min, recommend chlorthalidone.
 - 1. Starting dose 12.5mg once daily.
 - 2. Maximum dose 25mg once daily. However, dose adjustment is dependent on provider assessment of volume status. All follow-up

evaluations should be discussed with provider.

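### Appendix I: at potassium 5.0–5.4 after an ACEi/ARB start or increase, the tree continues the dose before testing the creatinine drawn with it against the written limits

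*Combined protocol and SAP*

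**What the plan says.** All of this is in Appendix I, ACEi/ARB PROTOCOL, unless stated otherwise.

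- **Timing of the laboratory check.** The Follow-Up item reads "Schedule RN BP Assessment Visit and Cr/K Check 1-3 weeks following initiation or dose increase", and then "Request patient to have labs drawn prior to appointment". The protocol defines a Cr/K Check as both tests, so the creatinine result is meant to be available with the potassium result.
- **Potassium is read first.** Above 5.4, the nurse discusses stopping the drug with the provider. At 4.9 or below, the nurse goes straight to the creatinine step.
- **The band between.** Above 4.9 but not above 5.4, the instructions are "Continue ACEi/ARB at current dose", a diet handout, and "Order repeat POTASSIUM LEVEL in 1 week". Then "If K is not < 5.0 on repeat evaluation, discuss with provider"; otherwise "If K is </= 4.9, proceed to Cr Interpretation".
- **The creatinine step.** It asks "Is Cr >20% higher than value prior to initiation or last increase of ACEi/ARB" and, if not, "Is creatinine within 30% of baseline since initiation". Exceeding either limit leads to a provider discussion about halving the dose (or stopping, at the starting dose) and about creatinine follow-up. Passing both leads to RN BP Assessment, where a further dose increase can be proposed.

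**The concern.** Within the 5.0–5.4 band, nothing tells the nurse to look at the creatinine already drawn before continuing the drug. The order of the steps therefore gives an odd result: a patient whose potassium and creatinine are both raised meets the explicit creatinine rule later than a patient whose creatinine alone is raised, or does not meet it in the written tree at all.

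Safety is what is at stake. Every enrolled patient has CKD, the appendix lists hyperkalemia and loss of kidney function among the effects to watch for with both recommended drugs, and Section 9.1 counts hyperkalemia and acute kidney injury among the events that its interventions might cause. This is an explicit sequence that the nurse is asked to follow, so it is more than a missing detail.

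**Working it through.** The plan states no figure for this point, so there is none to reproduce. The check is a walk through the written tree.

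**Inputs** (Appendix I, ACEi/ARB PROTOCOL): joint check at 1–3 weeks after the dose step; potassium cuts at 4.9 and 5.4; repeat of potassium alone after 1 week; creatinine limits of 20% and 30%. Assumptions: potassium is reported to one decimal, so the middle band is 5.0–5.4, and results are acted on at the scheduled times.

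| First K | Repeat K | Action at the first reading | When the creatinine limits are applied |
|---|---|---|---|
| 4.9 or below | none | creatinine step | 1–3 weeks after the dose step |
| 5.0–5.4 | 4.9 or below | continue, handout, repeat K | 1 + 1 = 2 to 3 + 1 = 4 weeks |
| 5.0–5.4 | 5.0 or above | continue, handout, repeat K | not reached; provider discussion at 2–4 weeks |
| above 5.4 | none | provider discussion about stopping | not reached; provider involved at 1–3 weeks |

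Deferral in the second row: (2 to 4) − (1 to 3) = 1 week.

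**Illustration.** Take creatinine 25% above its value before the dose step (an assumed figure). Since 25 > 20, the first limit is exceeded.

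- With K 4.8, dose reduction or stopping is discussed at the first reading.
- With K 5.2 and a repeat of 4.9, the dose continues and the same discussion comes 1 week later. The repeat is potassium only, so the creatinine then judged is the earlier one unless someone orders another.
- With K 5.2 and a repeat of 5.0, the provider is consulted 1 week later under an instruction that does not mention creatinine.

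**Could the pre-visit GFR rule fill the gap?** RN BP ASSESSMENT, Pre-Visit Planning, sends a GFR more than 20% below the previous value to the provider. That planning is done 1–2 weeks before the appointment. For a visit 1–3 weeks after the dose step, and not before the step that books it, planning falls from max(0, 1 − 2) = 0 to 3 − 1 = 2 weeks after the step. The blood draw is fixed only as before the appointment. The documents therefore do not show whether this comparison sees the new result.

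**The case against.** The strongest reply is that the provider can hear of a creatinine rise at the same visit anyway. Item f, under Home Blood Pressure Log Review, has the nurse check class effects at every visit and take any new one to the provider; reduced kidney function is a listed class effect. That route has no threshold, so it is wider than the 20% rule. Section 9.2.5 sends abnormal laboratory findings to the primary care provider under local procedures. A PA or NP assists and may suggest departures, and the provider selects and orders all medication. Even the creatinine step only starts a discussion.

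In addition, the dose is held, and within the follow-up tree it can be doubled only after both creatinine limits have been passed. The care protocols are optional for practitioners (Section 6.5), and adverse events are reviewed at least monthly (Section 9.3).

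Most of this stands, and it is why the severity is low. It does not remove the point: item f and Section 9.2.5 carry no creatinine limit, the pre-visit GFR rule may precede the new result, and none of these provisions tells the nurse to apply the limits before continuing.

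A reader might also infer that this band is the one place where kidney function goes unread. The text does not support that. Above 5.4, the provider discussion does not name creatinine either. In the DIURETIC PROTOCOL, a potassium that is not above 3.4 goes to the provider without reaching the GFR limit. What sets the 5.0–5.4 band apart is narrower: at the first reading, it prescribes neither a provider discussion nor the creatinine step.

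Finally, the extracted numbering of these steps is damaged, and the parent CKD protocol that initiates the appendix is not in the documents. The wording that links the repeat potassium to the creatinine step is intact, but the parent protocol might contain a further check.

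**Conclusion.** The point holds as a matter of sequence. At K 5.0–5.4, the explicit creatinine limits are applied about 1 week later when the repeat K is 4.9 or below, and are not reached in the written tree when it is 5.0 or above.

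Three stronger readings are not supported. The tree does not raise the dose over an unread creatinine. The 1 week is a delay in applying these limits, not in every possible escalation. It is also not a fixed delay for everyone in the band, because it depends on the repeat potassium.

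The conclusion rests on the visible text, on potassium to one decimal and on the stated intervals being kept. How often both values are raised together is not given, so neither a number of patients nor a harm can be estimated. I class this as a cheap patient-safety improvement of low severity, with no bearing on randomisation, the endpoint, sample size or the primary analysis.

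**What to change.** Change the 5.0–5.4 branch as follows, and leave the other two potassium branches as they are:

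1. Before continuing the dose, test the creatinine from the same Cr/K Check against both existing limits.
2. If either limit is exceeded, discuss potassium and creatinine with the provider at that reading.
3. If both are met, continue the dose, give the diet handout and repeat potassium in 1 week.
4. If the repeat is 4.9 or below, go to RN BP Assessment. If not, discuss potassium and creatinine with the provider.

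This removes the 1-week deferral and names creatinine in the branch that now omits it. It needs no new test and no new threshold. The cost is a wording change that all IRBs must approve before use (Section 14.2), and possibly some additional provider discussions, whose number is unknown. The appendix is due for review every year, which gives a natural occasion.
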